### **Data Analysis**

We first discuss general issues and then turn to analyses specific to the aims of the proposed research.

**Missing Data.** In general, missing data is infrequent and not problematic, but occasions may arise where this must be formally addressed. Data can be missing at random (MAR), missing completely at random (MCAR) or missing in a systematic way. To gain perspective on the nature of the missingness for a given variable, we will create a dummy variable coded for each respondent: 1 = missing value on the variable or 0 = not missing. We will test for associations between this variable and others in the models. We also will apply Little's multivariate test for MCAR. Missing data also can result from attrition. We will differentiate these two sources of missingness and explore for each. We will use Full Information Maximum Likelihood (FIML) and multiple imputation (MI) or systematically model missing data bias, depending on the data and the models.

**Assumption Violations.** We will use bootstrapping to derive asymmetrical confidence intervals or robust methods to address assumption violations. Mplus offers algorithms for both. In general, we will be sensitive to assumption violations and explore data cautiously.

**Outliers.** We will apply standard methods for outlier detection (e.g., analysis of leverage statistics, residuals, and dfBetas) and also use graphical approaches.

**Multiple Items, Variables, and Contrasts.** For all of our multi-item measures, we will evaluate the coefficient alphas and factor structures to ensure they are consistent with their psychometric histories. We will examine the intercorrelations and the results of exploratory or confirmatory factor analyses to guide choices about combining indices or latent constructs. When we conduct multiple significance tests, we will compare the robustness of our conclusions both with and without statistical corrections for multiple tests using the strategy discussed in Jaccard & Guilamo-Ramos. In general, we will use a Holm adjusted modified Bonferroni method or the False Discovery Rate (FDR) method for controlling experiment-wise error, both of which are more powerful than Bonferroni methods.

**Specification Error.** We will be sensitive to issues of specification error, being careful to explore a wide range of model diagnostics to protect against gross model misspecification.

**Measurement Error.** Where possible, we will adopt strategies that explicitly model measurement error (e.g., use multiple indicators in SEM). For single indicator models, measurement error can be modeled by fixing error variances of measures at a priori specified values that map onto the reliability of these measures suggested by previous research. If it is a multi-item measure, we can create multiple indicators using split-half methods. In cases where we cannot formally model measurement error influences, we will take care to recognize biasing effects of measurement error when interpreting the results of statistical analyses.

**Covariates.** In our modeling efforts, there may be confounds with some of our core explanatory variables. These confounds will be addressed by statistically controlling for them as covariates in our estimating equations. The choice of covariates is non-trivial, and one must be careful not to engage in atheoretical

partialling. Our approach will be to control if: (1) it is thought to be a source of spuriousness, and/or (2) it is correlated with the key variable(s) in the model but is thought to have an independent effect on the criterion. We will carefully consider the role of variables and explore models as is theoretically appropriate.

**Traditional SEM Analyses.** Many of our analyses will use structural equation modeling (SEM). A useful computer program for analyzing complex SEM is Mplus. It offers bootstrapping, robust standard errors, and numerical strategies to deal with mixtures of categorical and continuous endogenous variables. The models tested will generally be statistically over-identified. We will evaluate model fit using both global indices (chi square, the Bollen-Stine bootstrapped chi square, GFI, CFI, standardized RMR, RMSEA, and p-value for the test of close fit) and focused indices of fit diagnostic of specific points of ill fit (standardized residuals for predicted minus observed variances and covariances, modification indices, the presence of offending estimates, etc.). We will compare results of traditional modeling (maximum likelihood) with those from robust standard errors and bootstrapping. We will have increased confidence in coefficients in results across analytic methods. In the face of poor fit, we will examine diagnostics for revising the model that, first and foremost, are conceptually meaningful. Analytic strategies for interaction effects in complex SEM models are somewhat controversial. Mplus offers a quasi-maximum likelihood method that has desirable properties when data are multivariately normally distributed. Marsh et al. suggest a simple strategy for non-normal data, but which should be supplemented with limited simulation analysis to ensure one is not led astray by relaxed model constraints. [name] is skilled at the analysis of interactions in structural equation models and has co-authored several books on the topic. The strategies in Mplus and suggested by Marsh et al. will be pursued as well as limited information estimation approaches using traditional regression models.

[figure not shown]
**Randomization Bias.** We will assess differences at baseline between the groups (PN vs. controls) on major demographic and background variables (e.g., sex, age, education), and if necessary, add these as covariates to the analyses. In our past studies, we have not found significant differences between the groups on these variables when our sample sizes are at the numbers we have proposed (>75 per cell).

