**Parenting Now (PN).** REAL Prevention LLC (RP) adapted the Parent Handbook to digital format, Parenting Now (PN), and established its feasibility for a broader audience through a successful Phase I SBIR to address these limitations. In Phase II, our team will refine and complete PN based on our Phase I findings examining parents' preferences. These refinements include: 1) PN will have core modules that cover essential topics (e.g., why it is important for parents to talk with their students, improving communication, parent permissiveness toward adolescent drinking, how alcohol works in the body, and the difficulty of making

accurate judgments of impairment); 2) Customization, user-initiated tailoring, is accomplished through offering a menu of optional topics that parents can choose to acquire content specific to their interests (e.g., other commonly used substances that adolescents combine with alcohol use, parents' drinking and drug history, and the importance of being committed to a healthy lifestyle); and 3) Personalization, system-initiated tailoring, is accomplished through adapting content to the parent's communication style, based on the work of RP's [name]. Sundar's work demonstrates that both customization and personalization can improve engagement with digital materials, but that they work differently for different people. All the refinements are based on the findings of Phase I research and add to the innovation of the PN. We now seek to complete the PN adaptation, test its efficacy in a randomized control trial (RCT), and prepare it for rapid and widespread national and international dissemination via collaboration with D.A.R.E. America and other channels.

**Aim 1.** Toward this extent, Specific Aim 1 will conduct a RCT to evaluate PN's effects on youth alcohol use and other substance use assessed at 3 waves (baseline, 1 mo., and 6 mo.) using a rigorous study design that includes a nationally-representative sample and an active control condition.

**H1:** Students in the PN condition will engage in less alcohol use and consequences (primary outcome) than in the control condition.

**H2:** Students in the PN condition will engage in less marijuana use, nicotine use, and their combined use with alcohol (secondary outcome) than in the control condition.

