**Table 2. Measures Reflective of Theoretical Model in Figure 1**

Construct	Target	Time	alpha
Primary Outcomes			
Alcohol Use (Daily Drinking, HED, Quantity/Frequency, Peak) 	Teen	T1-T3	>.70-.90
Alcohol-related Consequences (e.g., Riding with a drunk driver) 	Teen	T1-T3	>.75-.85
Secondary Outcomes			
Marijuana Use 	Teen	T1-T3	>.70-.90
Nicotine Use (e.g., Cigarette Use; E-cigarette Use; Smokeless Tobacco) 	Teen	T1-T3	>.70-.90
Combined Substance Use	Teen	T1-T3	>.70
Tertiary Outcomes (Mediators)			
Parent Communication 	Parent,Teen	T2	>.75
Alcohol Motives/Expectancies/Willingness/Norms 	Teen	T2	>.70 - >.85
Moderators			
Background Demographics (Birth Sex, Gender Identity, Sexual Orientation, Age, Race / Ethnicity)	Teen	T1	–

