### **Specific issues and approaches for the analyses of the Specific Aims.**

**Aim 1: Evaluate the efficacy of PN intervention.** The primary focus of the analyses will document differences on our primary outcomes (alcohol use and alcohol-related harms) and secondary outcomes (marijuana use, nicotine use, and their combined use with alcohol) between the groups (PN/Control) using a mixed measures analysis of variance. A 2 X 3 (groups X time) MANCOVA will test the impact of the PN intervention on our outcome variables contrasting baseline tendencies against follow-up assessments (3 waves: baseline, 1 mo., and 6 mo.). For Aim 1 (analysis of efficacy), we will conduct an intent-to-treat analysis that will include all individuals who have been randomized to a condition. We will also examine differences in all outcomes by sex of the student (as a relevant biological variable), sexual orientation, and gender identity adding these as covariates to the analyses. We will be sensitive to inflated experiment-wise error rates and control these with modified Bonferroni methods.

**Aim 2: Examine mediators.** The second aim examines mediation paths in Figure 1 using SEM. We will follow the recommendations of MacKinnon (joint significance). For example, we will examine the relationship between the effects of the PN on predictors at the immediate post-PN assessment (1 mo. follow-up) and their subsequent effects on outcomes at the 6 month follow-up. The models will be statistically over-identified. We will examine global fit indices and focused indices of fit diagnostic of specific points of ill fit in the model (e.g., standardized residuals for predicted minus observed variances and covariances, and modification indices). We will use robust standard errors and bootstrapping. In the face of poor model fit, we will examine diagnostics that are conceptually meaningful and will significantly improve model fit.

[figure not shown]

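### The general multiplicity rule credits the False Discovery Rate method with experiment-wise error control that it does not give, and leaves open which result decides, so control for H1 is likely but not guaranteed.

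*Combined protocol and SAP*

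**What the plan says.** Two places in the Research Strategy govern multiple testing.

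- **Data Analysis, general issues (Multiple Items, Variables, and Contrasts).** "When we conduct multiple significance tests, we will compare the robustness of our conclusions both with and without statistical corrections for multiple tests". The default follows: "In general, we will use a Holm adjusted modified Bonferroni method" "or the False Discovery Rate (FDR) method" "for controlling experiment-wise error, both of which are more powerful than Bonferroni methods". There is no rule for choosing between the two methods, and none for the case where corrected and uncorrected conclusions differ.
- **Specific issues and approaches, Aim 1.** "We will be sensitive to inflated experiment-wise error rates and control these with modified Bonferroni methods". FDR is not mentioned, and Holm is not named.

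H1 belongs to Aim 1: "Students in the PN condition will engage in less alcohol use and consequences (primary outcome) than in the control condition". Table 2 lists the alcohol measures as "Alcohol Use (Daily Drinking, HED, Quantity/Frequency, Peak", with alcohol-related consequences as a further primary outcome. The Outcome Measures table (4.3) adds drunkenness. Teens are followed up at 1 and 6 months. Consequences are primary in the Specific Aims, H1, Objective 2 and Table 2, but secondary in the Outcome Measures table and in Statistical Design and Power. No section gives a numerical alpha or the list of tests that make up H1.

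**The concern.** Experiment-wise control limits the chance of making any false claim. FDR control limits the expected share of false claims among the claims made. The two agree when nothing is affected and separate once some outcomes respond, which is what the trial expects. The plan therefore attributes a property to a method that lacks it.

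The choice can also change the answer. Take five hypothetical p-values: 0.012, 0.018, 0.028, 0.035 and 0.20. Holm rejects none, because 0.012 exceeds 0.05/5 = 0.01. Benjamini-Hochberg rejects four, because 0.035 is below 0.05 × 4/5 = 0.04. With no correction, four are also below 0.05. The general rule allows all three results to be reported without saying which one carries the conclusion. The benchmarks section makes significant behavioral effects the most important indicator of success, and the Specific Aims tie dissemination to a successful evaluation.

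**Working it through.** **Inputs from the documents.** Two permitted methods plus an uncorrected comparison (Data Analysis); modified Bonferroni for Aim 1; four alcohol-use measures plus consequences in Table 2; two follow-ups; 280 dyads expected at 6 months (Participant retention); effects of 5–10% of outcome variance (Statistical Design and Power).

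**Assumptions.** Two-sided alpha 0.05; Benjamini-Hochberg as the FDR method; equal correlation of 0 or 0.5 between tests; families of 2, 5 or 10 tests (10 = 5 measures × 2 follow-ups); the number of real effects. The alpha is at least consistent with the plan's Aim 2 logistic example: (1.960 + 0.842)² / [0.2 × 0.8 × (ln 1.75)²] / (1 − 0.30²) = 172, against about 170 stated.

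**The plan's own figure.** It claims power above 0.80 for an effect of 5% of variance with about 200 per group. With f² = 0.05/0.95, N = 400 and a 1-df noncentral F test, power is 0.996, so the claim reproduces. No experiment-wise error figure is stated that could be reproduced.

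**No correction, no real effect.** Independent tests give 1 − 0.95^m: 0.098 for 2 tests, 0.226 for 5, 0.401 for 10. At correlation 0.5, simulation gives 0.09, 0.18 and 0.29.

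**Why FDR exceeds 5%, by hand.** Suppose 5 of 10 effects are real and all are detected. The next smallest p-value is compared with 0.05 × 6/10 = 0.03. Five independent null tests at 0.03 give 1 − 0.97⁵ = 0.141. Holm at the same step uses 0.05/5 = 0.01, giving 1 − 0.99⁵ = 0.049. For 5 tests with 2 real, FDR compares with 0.05 × 3/5 = 0.03, giving 1 − 0.97³ = 0.087.

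**Simulation** (at least 200,000 sets per row). Real effects have mean z = √(280 × 0.05/0.95) = 3.84. Entries are the chance of at least one false claim, at correlation 0 / 0.5.

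| Tests (real effects) | No correction | FDR | Holm |
|---|---|---|---|
| 2 (0) | 0.097 / 0.090 | 0.051 / 0.048 | 0.050 / 0.047 |
| 2 (1) | 0.050 / 0.050 | 0.049 / 0.048 | 0.048 / 0.047 |
| 5 (0) | 0.227 / 0.181 | 0.051 / 0.044 | 0.050 / 0.041 |
| 5 (2) | 0.142 / 0.125 | 0.084 / 0.072 | 0.047 / 0.040 |
| 5 (4) | 0.050 / 0.050 | 0.049 / 0.046 | 0.045 / 0.040 |
| 10 (0) | 0.403 / 0.287 | 0.051 / 0.042 | 0.049 / 0.038 |
| 10 (5) | 0.227 / 0.183 | 0.136 / 0.105 | 0.044 / 0.035 |

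With a smaller mean z of 3.3 (about 91% power per real effect), the 10-test, 5-real row gives FDR 0.126 / 0.090 and Holm 0.040 / 0.033. FDR values of 0.051 with no real effect are simulation noise around 0.05. The inflation needs at least one real effect and at least two null ones.

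**Power under Holm.** Effect of 5% of variance, 280 completers, 1 df: 0.969 at alpha 0.05; 0.893 at 0.05/5 = 0.01; 0.843 at 0.05/10 = 0.005.

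**The case against.** The strongest reply is that H1 has its own rule. The Data Analysis section says that it treats general issues first and then turns to each aim. The Aim 1 paragraph names modified Bonferroni methods, and the general section attaches that term to Holm alone, listing FDR separately. On that reading Holm governs H1 and the error is controlled. This largely stands. It does not close the point, because the Aim 1 paragraph does not name Holm, exclude FDR, give alpha, define the family or withdraw the comparison without correction. Outside Aim 1 only the general rule applies.

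Three further replies have force:

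- **Family size.** Ten tests is an assumption. The plan uses a MANCOVA and may combine measures after factor analysis. If H1 came down to two tests, FDR would not inflate the error. But no section limits it to two, and combining measures after seeing their intercorrelations leaves the family open.
- **What the error means.** A reader might infer that FDR makes it more likely that an inert PN is declared effective. It does not: if PN affects nothing, FDR stays at about 5% or below. The excess error consists of naming additional measures as affected when others truly are.
- **The uncorrected comparison.** "we will compare the robustness of our conclusions both with and without statistical corrections for multiple tests" reads as a sensitivity check, with corrected results as the default. The plan refers to a cited strategy for it, which cannot be consulted here. The plan itself does not say what happens when the two disagree.

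**Conclusion.** The description of FDR in the general section is wrong. With 5 to 10 tests and some real effects, the chance of at least one false claim is about 7% to 14% in the main scenarios, against at most 5% for Holm. That range rests on the assumed alpha, FDR procedure, correlations, family size and number of real effects. There is no inflation if PN affects nothing, if there are two tests, or if only one outcome is unaffected.

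A reader might conclude that the plan fails to deliver an error rate claimed for H1. The documents do not support that: no numerical rate is stated, and the Aim 1 paragraph points to Holm. The supportable conclusion is that control for H1 is not guaranteed, because the general rule leaves FDR and an uncorrected reading available with no deciding rule. This should be fixed, but it does not invalidate the design.

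**What to change.** 1. In Multiple Items, Variables, and Contrasts, delete FDR from the sentence on experiment-wise error.
2. Align that paragraph with the Aim 1 paragraph: claims for H1, and for any other hypothesis labelled primary (H3 carries that label), rest on Holm-adjusted p-values at a stated alpha.
3. List the family for each such hypothesis: measures, time points, and whether consequences belong to it, settling their primary or secondary status throughout.
4. Where FDR is used outside the primary hypotheses, describe it as FDR control.
5. State that uncorrected p-values are descriptive and cannot support a claim.

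The change is to wording only and needs no additional participants or data. The power cost at Holm's strictest step is a fall from 0.97 to 0.89 for five tests or 0.84 for ten, for an effect of 5% of variance with 280 completers. Both remain above the 0.80 that the plan states, so FDR is not needed to protect power.

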**Randomization.** GfK starts with estimates for survey completion rate, incidence (confirmation of teen’s age and consent), and the number of subgroups. These estimates are used to determine the estimated number of eligible parents who have children of study age. GfK then selects the sample of parents from their panels. Parents are then screened for eligibility and consented. Parents that provide consent are assigned numbers based on a random number table sequence and then randomly assigned to one of the study arms.

**Data Collection and Measurement.** As noted above, self-report surveys programmed and facilitated by GfK will be completed online, at up to 3 timepoints: baseline and 1- and 6-months post intervention (Table 2). In addition, program analytics will be examined to help ensure fidelity to the intervention, and to be included as covariates in all analyses.

**Self-Report.** Table 2 describes the self-report measures to be assessed, consistent with our conceptual model depicted in Figure 1, including primary, secondary, and tertiary outcomes. As indicated above, both teens and parents will complete online surveys through GfK. This self-report methodology is consistent with major national epidemiological surveys of teen substance use, as well as [name]’s prior work in this area, and is demonstrated to be valid. Participants will be made aware of the importance of the data, the confidential nature of their responses, and that the research team will follow appropriate procedures to secure their privacy.

PN Program Analytics. Program analytics (i.e., log data) to be collected include total time spent accessing PN, time spent on each module and activities within modules, and number of activities and modules completed. These data will be captured through HTML5 programming and downloaded into Excel. From this data, we will be able to examine the depth of parents’ immersion in the program and distinguish between users who quickly moved through the program versus those with a deeper level of engagement as well as assess accuracy and use them to assess effects of program exposure (i.e., dose).

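### Adjustment for demographic and background variables rests on an undefined baseline-difference check, and the covariates of the primary Aim 1 model are not fixed in advance

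*Combined protocol and SAP*

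**What the plan says.** The Randomization Bias paragraph (Data Analysis) states: "We will assess differences at baseline between the groups (PN vs. controls) on major demographic and background variables". Its examples are sex, age and education, given as an open list. Variables that differ may then enter the model: "and if necessary, add these as covariates to the analyses". No test, threshold or imbalance measure is given. The next sentence reports that in past studies "we have not found significant differences between the groups on these variables", which suggests a significance check but does not say so.

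The efficacy model is in the section on analyses of the Specific Aims, under Aim 1: "A 2 X 3 (groups X time) MANCOVA will test the impact of the PN intervention on our outcome variables". It contrasts baseline with the two follow-ups, so the baseline outcome is one of its three waves. Its covariates are not listed.

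Other sections open further routes into the model:

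- **Aim 1** adds student sex, "sexual orientation, and gender identity adding these as covariates to the analyses", with no baseline-difference condition, in the sentence on examining outcome differences by those variables.
- **Covariates** (Data Analysis) controls for a variable thought to be a source of spuriousness, or where "it is correlated with the key variable(s) in the model but is thought to have an independent effect on the criterion". This is a matter of judgement, not a list.
- **Attrition analyses** adds a drop-out indicator if its correlation with key variables is non-trivial, with 0.2 as the example.
- **Data Collection and Measurement** says program analytics are "to be included as covariates in all analyses". These are logged after randomization.

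**The concern.** Under correct randomization any baseline difference between arms is due to chance. A check for such differences therefore cannot tell the analyst which covariates to include. What matters for precision is how well a variable predicts the outcome, and that can be judged before the data are seen.

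The larger problem is that the primary model is not determined. The trigger is undefined, the variable list is open, and the other routes are partly judgement and partly data-driven. Two careful analysts following the plan could fit different Aim 1 models to the same data, and the choice could be made after seeing which one favours Parenting Now. For sex the two paragraphs disagree outright: one makes adjustment conditional and the other does not.

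**Working it through.** **Inputs from the documents.** 400 dyads, 1:1 (Randomized Trial Design; Participant Recruitment and Procedures). 320 and 280 dyads expected at 1 and 6 months (Participant retention). Power above 0.80 for effects of 5–10% of outcome variance with about 200 per group (Statistical Design and Power).

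**Assumptions, because the documents give no figure.** Two-sided alpha 0.05; p<0.05 as the baseline trigger; the share of outcome variance explained by covariates; the correlation r between baseline and follow-up; a 0.3 SD effect for the sensitivity case.

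**1. The plan's own power figure.** Noncentral F with 1 numerator df and f² = R²/(1−R²). For R² = 0.05, f² = 0.0526 and d = 2√f² = 0.459. Power is 0.996 (N=400), 0.984 (N=320) and 0.969 (N=280). At R² = 0.10 it is at least 0.9998 for all three. The stated figure of more than 0.80 is reproduced.

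**2. How often chance alone sets off the check.** P(at least one difference at p<0.05) = 1 − 0.95^k for k independent covariates.

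| k | Probability |
|---|---|
| 3 | 0.143 |
| 5 | 0.226 |
| 8 | 0.337 |

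**3. Type I error.** Simulation with 6,000 null trials per setting, 200 or 140 per arm, three independent normal covariates jointly explaining 5%, 10% or 30% of variance, and one normal follow-up outcome. Monte Carlo standard error is about 0.003.

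| Analysis | Null rejection rate |
|---|---|
| Fixed rule: add each covariate with baseline p<0.05 | 0.043–0.051 |
| Better of the unadjusted and fully adjusted results | 0.058–0.080 |

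The fixed rule holds its level and is slightly conservative when the covariates are strongly prognostic. The inflation comes from free choice between results. Only two candidate models were compared.

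**4. Precision at 6 months.** With n = 140 per arm and unit outcome variance, the residual variance v is 2(1−r) for a change-from-baseline contrast, which is the closest simple analogue of the group-by-time test. It is 1−r² when baseline is a covariate. The noncentrality is λ = d√(n/(2v)), on 278 df. With d = 0.3:

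| r | v, change | λ | Power | v, baseline as covariate | λ | Power |
|---|---|---|---|---|---|---|
| 0.5 | 1.00 | 2.51 | 0.71 | 0.75 | 2.90 | 0.82 |
| 0.6 | 0.80 | 2.81 | 0.80 | 0.64 | 3.14 | 0.88 |
| 0.7 | 0.60 | 3.24 | 0.90 | 0.51 | 3.51 | 0.94 |

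In simulation, adding demographics to the baseline-adjusted model gives about 0.83, 0.88 and 0.94, so nearly all the gain comes from the baseline outcome. Adding demographics to the change contrast gains essentially nothing, because stable characteristics largely cancel in a difference.

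**5. The same comparison at the planned effect.** With d = 0.459 and r = 0.5, power is 0.97 for the change contrast and 0.99 with baseline as a covariate. At r = 0.6 and 0.7 the change contrast already has power of 0.99 or more.

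**The case against.** The case against has several parts, and most of it stands.

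- **The check is not the only way in.** A reader might infer that covariates enter the efficacy model only if the arms differ. The documents do not support that: Aim 1, the Covariates paragraph and the program-analytics sentence all add variables without that condition. What remains is that these routes do not close the model either. They add to its openness.
- **No large power loss can be pinned on the check.** A reader might infer one by treating baseline drinking as a variable the check controls. The paragraph covers demographic and background variables, and baseline drinking is already the first wave of the MANCOVA. Eligible teens are aged 16–17, so age is unlikely to be strongly prognostic. The gain in step 4 comes from how the baseline outcome is used, not from removing the check.
- **The baseline test does not inflate false positives.** A reader might infer that it breaks the nominal level. Applied as a fixed rule it does not (step 3).
- **The plan is powered for larger effects.** At 5% of variance, unadjusted power with 280 dyads is already 0.97. The 0.3 SD effect is an assumption of this review, not the plan's.
- **Adding the baseline outcome to the 2 × 3 model would use it twice.** This is correct, and the fix avoids it.

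**Conclusion.** The concern holds as a pre-specification problem. Adjustment for demographic and background variables depends on an undefined check over an open list, the covariates of the primary Aim 1 model are fixed nowhere, and the two statements about sex must be reconciled. The harm that can be quantified is analyst choice: type I error of about 6% to 8% when the better of two results may be reported. This rests on normal outcomes, three independent covariates explaining 5% to 30% of variance, and a model without the baseline wave.

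The precision gain is secondary and conditional. It is 4 to 12 percentage points of 6-month power at 0.3 SD with r between 0.7 and 0.5, and about 2 points or less at the planned effect. It assumes that a change contrast represents the planned group-by-time test, and that the outcome is roughly continuous and normal.

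**What to change.** 1. Delete the baseline-difference check as a trigger for adjustment. Report baseline balance descriptively, without p-values.
2. Name one covariate set for the primary Aim 1 model, used whatever the observed balance: teen sex, age and race/ethnicity, plus the baseline value of the outcome. Take the 1- and 6-month values as the outcomes, so that baseline is not used twice.
3. Pool sparse race/ethnicity categories by a rule written in advance. The planned enrolment table has categories of 3 and 5 people.
4. Align the Randomization Bias and Aim 1 text on sex. State that the judgement-based covariates, the drop-out indicator and the post-randomization program analytics belong to labelled secondary or sensitivity analyses, not to the primary intent-to-treat model.

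The cost is SAP wording. Table 2 already collects the outcomes and these demographics from teens at T1, so no new data are needed. The Aim 1 model statement changes from three repeated waves to two follow-ups adjusted for baseline, and the power text should describe the same model.
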